## 10.2 Correlative Studies

The degree of nuclear AR expression levels will be determined using standard immunohistochemistry methodology on all tissue and reported as percent tumor cells with nuclear AR staining. One-three 5 micrometer superplus frost slides will be used for IHC testing. This testing will be performed at the Memorial Sloan-Kettering Cancer Center CLIA approved Clinical Laboratory using the Dako androgen receptor antibody. Upon receipt of the slide in the clinical laboratory, results will be reported within 48 hours. The relationship between tumor response and degree of AR expression, and/or AR signaling, will be examined. Additional assays for AR signaling, (e.g., gene expression array analyses, mutation analyses, or other immunohistochemistry evaluations) may be performed on remaining tissue to evaluate for molecular phenotypes and patterns associated with activated AR signaling.

Germline DNA will be used both for cell free DNA analysis and as a matched normal for MiSeq analysis. MiSeq will be used to evaluate for alterations within the androgen, estrogen, and progesterone receptors. Germline DNA from peripheral blood will be used to filter out germline variants. The germline DNA sequencing data will be used as a filter to define somatic alterations and will not be reported. A 10cc tube of whole blood will be collected on Cycle 1, Day 1 and on Cycle 2, Day 1 for use in gene expression analyses. This testing will be performed at Memorial Sloan-Kettering Cancer Center.

Archived patient blood and/or tissue may be sent to Medivation Inc. and/or Astellas for additional analyses.

Any additional future studies performed using the clinical information, blood, or tissue collected from this study will only be performed after completion of appropriate institutional approval.

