## 2.1 OBJECTIVES AND SCIENTIFIC AIM

Primary Objective:

- To estimate the proportion of women with AR(+) ovarian, primary peritoneal, or fallopian tube cancer who survive progression free for at least 6 months and the proportion of patients who have objective tumor response (complete or partial response) by RECIST 1.1 criteria when treated with enzalutamide 160 mg PO QD.

Secondary Objective:

- To determine the frequency and severity of adverse events as assessed by NCI CTCAE version 4.0 in women with AR (+) ovarian, primary peritoneal, or fallopian tube cancer treated with enzalutamide 160 mg PO daily.

Exploratory Objective:

- To perform optional tumor biopsies following treatment with enzalutamide, in order to determine the effect of treatment with enzalutamide on androgen receptor expression
- To observe the effect of enzalutamide on serum testosterone and estradiol levels in women with AR+ ovarian, primary peritoneal, or fallopian tube cancer.

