### **3.2 Enzalutamide**

Enzalutamide is a novel small molecule androgen-receptor antagonist selected for its activity against cells overexpressing the androgen receptor [23]. Enzalutamide has a novel mechanism of action that is unlike that of bicalutamide and has been shown in preclinical studies to provide a more complete suppression of the antiandrogen receptor pathway than bicalutamide. Enzalutamide slows growth and induces cell death in AR expressing cells via three complementary actions. Enzalutamide blocks testosterone binding to the androgen receptor, impedes nuclear translocation of the androgen receptor, and inhibits binding of DNA. Preclinical data have demonstrated that enzalutamide is superior to bicalutamide in each of these three actions.

In a mouse xenograft model of prostate cancer using an androgen receptor overexpressing cell line, Enzalutamide treatment resulted in a dose-dependent reduction in tumor volume ( $p < 0.05$  and  $p < 0.01$  for mid-and high-dose groups vs. vehicle, respectively). Enzalutamide treatment resulted in unmeasurable tumors in 1/7 animals in the low-dose group and 3/7 animals in the high-dose group. As expected, bicalutamide had little effect on tumor growth.

Enzalutamide binds with high affinity to the human androgen receptor ( $K_i = 13$  nM). Other targets for which measurable enzalutamide binding was detected included the human progesterone receptor with a 50% inhibitory concentration ( $IC_{50}$ ) of 10-25  $\mu$ M and the rat gamma amino butyric acid-gated chloride channel ( $IC_{50} = 2.6$   $\mu$ M;  $K_i = 2.1$   $\mu$ M [1.0  $\mu$ g/mL]). No significant binding was detected with the remaining 70 receptors.

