### **3.3 Previous Human Experience with Enzalutamide**

The safety and tolerability of enzalutamide have been evaluated in numerous clinical studies in both healthy adult male volunteers and in male patients with prostate cancer. The duration of exposure ranges from a single dose to more than 4 years. The estimated safety, PK, and tolerability are based primarily upon the data collected from the completed Phase 1-2 study (S-3100-1-01).

Study S-3100-1-01 was an open label, dose-escalation study of enzalutamide in 140 patients with advanced prostate cancer. Patients were treated with enzalutamide at doses of 30 to 600mg/day until disease progression or intolerable side effects developed.

In this study, enzalutamide was absorbed rapidly after oral administration, with the median time to Cmax after a single dose occurring at 1 hour (range 0.42 to 4 hours postdose). No major deviations from dose proportionality were observed over the dose range of 30 to 600mg. Due to the long t1/2 (~5.8 days), it took approximately 1 month to reach steady state. With daily oral administration, enzalutamide accumulated approximately 8.33-fold relative to a single dose. The peak-to-trough ratio was approximately 1.25, indicating that the average difference between the peak and trough concentrations was ≤ 25%. As a result of the low daily fluctuations, plasma profiles at steady-state resembled a constant infusion. The trough values in individual patients remained constant beyond Day 28 of chronic therapy, suggesting time-linear PKs once steady state was achieved.

Grade 3/4 adverse events reported by at least 3% of patients were fatigue (14%), anemia (4%), and back pain (3%). Fatigue was the most frequently reported adverse event, with dose-dependent increases of Grade 3 fatigue (0% at 150mg/day, 9% at 240 mg/day, 15% at 360mg/day and 20% at 480 mg/day). At doses of 240 mg and above, an increasing proportion of patients needed dose reductions for fatigue (1 of 29 patients [3%] who received 240mg/day, 3 of 28 patients [11%] who received 360mg/day and 5 of 22 patients [23%] who received 480mg/day, compared with 0 of 59 patients who received 30, 60 or 150 mg/day). After dose reductions, the symptoms resolved. Only 1 patient discontinued treatment due to fatigue with an onset coinciding with prostate-specific antigen (PSA) rise. The dose of 240mg/day was defined as the maximum tolerated dose.

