### **10.1.b Tumor Biopsy**

Tumor biopsies will be performed at two time points during this study; a biopsy will be performed at screening if no archival tissue is available and an optional biopsy will be performed at end of treatment.

If the patient has archival tissue available that is appropriate for AR IHC staining (block or unstained slides), then archival tissue may be used. In cases where multiple blocks are available staining will be performed on unstained slides from 3 separate blocks. If  $\geq 5\%$  AR tumor staining is seen on  $\geq 1$  slide the tumor will be considered to be AR+.

An optional tumor biopsy will be performed at end of treatment in those patients who have POD, consent to biopsy, and have accessible disease.

Biopsy samples should be fixed in 10% formalin and paraffin embedded. **In cases where a reasonable size biopsy is obtained (i.e., excisional biopsy, 18 gauge needle), such that the pathologist feels there is adequate sample for preparation of both a frozen and fixed specimen, a fresh frozen biopsy should also be collected.** At a minimum, enough tissue should be collected (by FNA or Core) for generation of a FFPE block for H&E and IHC analysis. At a maximum 2 cores should be collected.

Lesions with the greatest change in dimensional size based on interval evaluation are the recommended lesions to be excised. Whenever possible, biopsies at POD should be performed within 3 days of study drug discontinuation.

Biopsies obtained at the time of progressive disease will be used to investigate potential mechanisms of acquired resistance. Biopsy samples will be analyzed for level of AR positivity by IHC in order to determine if the androgen receptor is downregulated during treatment with enzalutamide.

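### A fall in nuclear AR staining on the end-of-treatment biopsy cannot be read as downregulation, because enzalutamide may itself lower nuclear AR and no total-AR score is planned

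*Combined protocol and SAP*

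**What the plan says.** Section 2.1 includes, as an exploratory objective, optional biopsies after treatment "in order to determine the effect of treatment with enzalutamide on androgen receptor expression". Section 10.1.b makes the question specific: samples are stained for AR "in order to determine if the androgen receptor is downregulated during treatment with enzalutamide". The same section limits the end-of-treatment biopsy to consenting patients with progression and accessible disease, and sets a target time: "Whenever possible, biopsies at POD should be performed within 3 days of study drug discontinuation".

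Section 10.2 fixes the measure. Nuclear AR is to be determined on all tissue and "reported as percent tumor cells with nuclear AR staining". Neither a cytoplasmic score, a score for any compartment, nor a staining intensity is committed to. Section 10.2 allows further assays on leftover tissue, including other immunohistochemistry, but they are optional, directed at AR signaling, and not specified as measuring total AR.

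Section 3.2 says that the drug, among its three actions, "impedes nuclear translocation of the androgen receptor". Section 14.3 plans graphs and descriptive statistics for the change in tumour AR.

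**The concern.** The objective concerns how much receptor the tumour expresses. The measure records whether receptor is seen in the nucleus. By the protocol's own account of the mechanism, enzalutamide can change the second without changing the first, and the biopsy is wanted at a time when much of the drug remains.

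The interpretation of resistance is at stake. Loss of receptor in a progressing tumour would suggest that the target has gone. Receptor still present but kept out of the nucleus would suggest that the target remains and that resistance arises elsewhere. Both appear as a lower nuclear percent. The problem is distinct from the age of the baseline tissue and would remain with a fresh baseline biopsy.

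**Working it through.** **Is drug still present at the biopsy?** Inputs, from Section 3.3 (Previous Human Experience with Enzalutamide): half-life about 5.8 days; steady state in about 1 month; with daily dosing, "enzalutamide accumulated approximately 8.33-fold relative to a single dose". From Section 10.1.b: a 3-day target. First-order elimination is assumed.

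1. *Reproducing the plan's figures.* Fraction of steady state at day t = 1 − 2^(−t/5.8). Day 28: 1 − 2^(−28/5.8) = 1 − 0.035 = 0.965. Day 29 (5 half-lives): 0.969. Both agree with about 1 month. Accumulation ratio = 1/(1 − 2^(−1/5.8)) = 1/(1 − 0.887) = 8.88, against the stated 8.33. A ratio of 8.33 implies a half-life of ln 2 / [−ln(1 − 1/8.33)] = 5.42 days, a difference that rounded or observed values could explain.
2. *Drug remaining t days after the last dose* = 2^(−t/5.8):

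| Days since last dose | Fraction of steady state |
|---|---|
| 1 | 0.89 |
| 3 | 0.70 |
| 7 | 0.43 |
| 14 | 0.19 |

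The level reaches 10% at about 19 days.

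3. *Sensitivity at day 3.* Half-life 5.42 days: 0.68. Assumed half-lives of 4 and 8 days: 0.59 and 0.77.

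A biopsy that meets the target is therefore taken under substantial drug exposure, and one taken a week or so late still is.

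**What can the nuclear percent identify?** Let A be the proportion of tumour cells with AR staining in any compartment, s the share of those cells with nuclear staining, and N = A × s the planned score. With 0 for baseline and 1 for end of treatment:

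N1/N0 = (A1/A0) × (s1/s0)

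The plan observes only the left side. If N falls, A may have fallen (less receptor), s may have fallen (receptor kept out of the nucleus), or both. One observed ratio cannot fix two unknown ones.

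The ambiguity runs one way. If the drug can only lower s, then s1/s0 ≤ 1 and A1/A0 ≥ N1/N0. When N is stable or higher, A has not fallen, so exclusion does not disturb that reading. The proportion of positive cells also says nothing about the amount of receptor per cell, so intensity is needed as well.

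The documents give no value for s1/s0. The contribution of exclusion could run from none to the whole of an observed fall.

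**The case against.** The best counter-argument is that the confounder is possible but not shown. Section 3.2 says that the drug hinders translocation, not that it abolishes it. A cell that keeps part of its receptor in the cytoplasm may still be scored nuclear-positive. The half-life comes from men with prostate cancer, and nothing links plasma level to the proportion of nuclear-positive cells. Biopsied tumours have progressed on drug, so translocation may no longer be hindered in them. The 3-day window is only a target. Section 10.2 leaves room for expression arrays and other immunohistochemistry, and leftover fixed tissue could be rescored later. The aim is exploratory, with no test or decision rule.

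All of this stands as a limit on the claim. A reader might infer that every biopsied patient's result is biased towards downregulation, that the objective cannot be answered at all, or that 70% residual drug means 70% nuclear exclusion. The documents support none of these: they give no size for the effect, only a fall is ambiguous, and drug level is not a measure of receptor location. Nor do they show that a fall would mean the drug was still working.

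The objection does not remove the core. The only committed measure is nuclear, the conclusion drawn from it is worded as downregulation, and no named assay separates amount from location. Tissue for optional assays is also scarce, since Section 10.1.b allows at most 2 cores and accepts fine-needle aspiration.

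**Conclusion.** The point holds as a low-severity, cheaply corrected weakness. If nuclear percent falls between baseline and end of treatment, the committed readout cannot tell loss of receptor from receptor kept out of the nucleus. Drug exposure at a biopsy meeting the target is about 70% of steady state on day 3 (59% to 77% for assumed half-lives of 4 to 8 days), and higher if it is taken sooner. The effect of that exposure on nuclear staining is unknown.

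The conclusion rests on the mechanism stated in Section 3.2, the half-life in Section 3.3 and first-order elimination. It does not touch the primary endpoints, sample size, eligibility or safety rules. The analyses in Section 14.3 that relate AR level to response and PFS are also untouched where they use tissue obtained before enzalutamide.

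**What to change.** Amend Sections 10.1.b, 10.2 and 14.3 as follows.

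- On the same stained baseline and end-of-treatment slides, record the percent of tumour cells with AR staining in any compartment (nuclear or cytoplasmic) and its intensity. Score each cell once: adding separate nuclear and cytoplasmic percentages would double-count cells positive in both.
- Base any statement of downregulation on that any-compartment score.
- Report nuclear percent separately, noting that it may reflect drug action.
- Leave eligibility scoring as it is.
- Have the laboratory confirm that cytoplasmic staining can be scored reliably with this antibody, which the documents do not address. If it cannot, report the result as change in nuclear AR and draw no conclusion about downregulation.

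The cost is a little more pathologist time per slide, with no new tissue or biopsy. The change does not cure a separate limitation: baseline tissue may be archival, and Section 3.1 says that AR positivity falls after chemotherapy. A fall in the any-compartment score could still not be attributed to enzalutamide alone.

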## **11.0 TOXICITIES/SIDE EFFECTS**

### **11.1 Most Frequent Adverse Events**

The safety and tolerability of enzalutamide have been evaluated in 13 studies. It is estimated that a total of 124 healthy volunteers, 16 subjects with hepatic impairment, and approximately 1800 patients with prostate cancer have been exposed to enzalutamide in completed, open-label, and ongoing blinded studies. No study has been terminated early for safety reasons.

Enzalutamide (160 mg daily) was generally well-tolerated in the placebo-controlled CRPC2 study of 1199 patients with progressive castration-resistant prostate cancer previously treated with docetaxel-based chemotherapy. The adverse events occurring in at least 5% of the enzalutamide group and at an incidence at least 2% greater than in the placebo group included fatigue (33.6% vs. 29.1%), diarrhea (21.4% vs. 17.5%), hot flush (20.3% vs. 10.3%), musculoskeletal pain (13.6% vs. 10.0%), headache (11.6% vs. 5.5%), insomnia (8.6% vs. 6.0%), anxiety (6.4% vs. 4.0%), hypertension (6.1% vs. 2.8%), and nasopharyngitis (5.1% vs. 3.0%).

Other adverse events reported less commonly than 5% but that may be associated with enzalutamide treatment after careful assessment of the adverse events include: falls (4.0% vs. 1.3%), dry skin (3.6% vs. 1.3%), and pruritus (3.5% vs. 1.3%). A possible cognitive effect of enzalutamide was observed with a greater proportion of patients in the enzalutamide-treated group (4.1% vs. 1.8%) reporting the following adverse events: memory impairment, cognitive disorder, amnesia, disturbance of attention, and dementia. In addition, events related to hallucination (visual hallucination, tactile hallucination, hallucination) were reported more frequently in the enzalutamide-treated group (1.6% vs. 0.3%).

During pre-market evaluation, seizure was identified as a risk associated with enzalutamide treatment. In the controlled clinical study, 5 patients (0.6%) experienced a seizure out of 800 patients treated with a daily dose of 160 mg enzalutamide, whereas no seizures occurred in patients treated with placebo. One additional serious adverse event reported by the Investigator as syncope was identified by the Sponsor as having several features suggesting seizure as the most likely diagnosis. Confounding factors may have contributed to the occurrence of seizures in several of these cases. Dose appears to be an important predictor of seizure, with a greater risk of seizure at daily doses higher than 160 mg. In a dose escalation study involving 140 patients, no patients experienced seizures at or below daily doses of 240 mg, whereas 3 seizures were reported, 1 each at 360, 480, and 600 mg/day.

Caution should be used in administering enzalutamide to patients with a history of seizures or other predisposing factors including, but not limited to, underlying brain injury, stroke, primary brain tumors or brain metastases, or alcoholism. In addition, the risk of seizure may be increased in patients receiving concomitant medications that may lower the seizure threshold. Enzalutamide should be permanently discontinued in patients who have a seizure while on treatment.

## 11.2 Safety Measurements

Safety and tolerability will be determined by frequent assessment of adverse events, physical examinations, vital signs, and safety laboratory assessments as defined in section 10.1. A safety follow-up visit will be conducted approximately 30 days after the last dose of enzalutamide.

## 12.1 CRITERIA FOR THERAPEUTIC RESPONSE/OUTCOME ASSESSMENT

Response and progression will be evaluated in this study using the international criteria proposed by the revised Response Evaluation Criteria in Solid Tumors (RECIST) guideline (version 1.1) [*Eur J Ca* 45:228-247, 2009]. Changes in the largest diameter (unidimensional measurement) of the tumor lesions and the shortest diameter in the case of malignant lymph nodes are used in the RECIST criteria.

## 12.2 Definitions

Evaluable for toxicity. All patients will be evaluable for toxicity from the time of their first treatment on study.

Evaluable for objective response. Only those patients who have measurable disease present at baseline, have received at least one cycle of therapy, and have had their disease re-evaluated will be considered evaluable for response. These patients will have their response classified according to the definitions stated below. (Note: Patients who exhibit objective disease progression prior to the end of cycle 1 will also be considered evaluable.)

Evaluable Non-Target Disease Response. Patients who have lesions present at baseline that are evaluable but do not meet the definitions of measurable disease, have received at least one cycle of therapy, and have had their disease re-evaluated will be considered evaluable for non-target disease. The response assessment is based on the presence, absence, or unequivocal progression of the lesions.

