Earlier studies examining alternative methods of androgen inhibition in ovarian, primary peritoneal, and fallopian tube cancer have all been performed in an unselected population of women, typically with multiple prior lines of therapy. Drawing on recent advances, the present study will be performed in a selected population of women with AR+ advanced ovarian, primary peritoneal, or fallopian tube cancer ( $\geq 5\%$  by IHC) with measurable disease. Enrolled patients will have had only one, two or three prior cytotoxic therapies. All enrolled patients will be treated with enzalutamide 160 mg PO QD until progression of disease (POD), unacceptable toxicity or withdrawal from study. Based on the prior response rates that have been seen with targeted therapy of recurrent or advanced ovarian cancer (Table 1), and the relatively benign side effect profile of enzalutamide, we will consider this treatment worthy of further study if there is an observed response rate of 12.5% or an observed 6 month PFS interval is seen in 22.5% of patients. Given that enzalutamide 160 mg PO has not previously been administered to women with ovarian cancer this study will utilize a safety lead-in. If  $\geq 5$  out of the first 15 patients develop a DLT during the first 28 days of treatment then the study will be put on hold. If this does not occur then enrollment will continue.

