If  $< 5$  patients develop one of the above events during the first 28 days of treatment then enrollment will proceed following a two-stage design. A total of 28 patients (including the first 15) will be enrolled during the first stage. If 3 or more patients have clinical response or 5 or more patients have no progression/death at 6 months, then the study will open to the second stage of accrual. No more than 9 out of the 28 patients (1/3) enrolled during stage I will have 3 prior therapies. In stage II, an additional 30 patients will be enrolled. At the end of stage II, if at least 7 of 59 (28+30=58) patients have clinical response or at least 13 of 59 patients survive progression free for 6 months, this will be considered as a positive trial.

Patients will be evaluated for radiographic response every 2 cycles (8 weeks) and at the end of study. Response is defined as the best over-all response achieved by RECIST 1.1 criteria while on study treatment.

At end of treatment an optional tumor biopsy will be performed in patients who consent to this procedure.

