**For Patients with Measurable Disease (i.e., Target Disease)**

Target Lesions	Non-Target Lesions	New Lesions	Overall Response	Best Overall Response when Confirmation is Required*
CR	CR	No	CR	≥4 wks. Confirmation**
CR	Non-CR/Non-PD	No	PR	≥4 wks. Confirmation**
CR	Not evaluated	No	PR	
PR	Non-CR/Non-PD/not evaluated	No	PR	
SD	Non-CR/Non-PD/not evaluated	No	SD	Documented at least once ≥4 wks. from baseline**
PD	Any	Yes or No	PD	no prior SD, PR or CR
Any	PD***	Yes or No	PD	
Any	Any	Yes	PD	

\* See RECIST 1.1 manuscript for further details on what is evidence of a new lesion.

\*\* Only for non-randomized trials with response as primary endpoint.

\*\*\* In exceptional circumstances, unequivocal progression in non-target lesions may be accepted as disease progression.

Note: Patients with a global deterioration of health status requiring discontinuation of treatment without objective evidence of disease progression at that time should be reported as “*symptomatic deterioration.*” Every effort should be made to document the objective progression even after discontinuation of treatment.

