The clinical response and the PFS from the starting of the treatment will be documented for each patient (including the patients in the safety lead-in). All the patients enrolled in this phase will be included in the main analysis of response and PFS. Patients who are lost to follow-up within 6 months are considered as failures for the PFS binary outcome of PFS within 6 months: yes/no. The response rate will be calculated. The patients accrued during the safety lead-in period will be included in the first stage of two-stage phase II portion. With the accrual rate of 3-6 patients per months, accrual of the 28 stage I patients should be complete within 9 months. After confirming promising results from stage I, the accrual of an additional 30 stage II patients should be complete within 10 months. The expected total trial duration is 30 months.

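### Does the evaluable-for-response definition in Section 12.2 leave room for an inflated primary response rate?

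*Combined protocol and SAP*

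**What the plan says.** Section 2.1 makes it a primary objective to estimate "the proportion of patients who have objective tumor response (complete or partial response) by RECIST 1.1 criteria". Section 12.2 Definitions then says who receives a response classification: patients with measurable disease at baseline who "have received at least one cycle of therapy, and have had their disease re-evaluated will be considered evaluable for response". It adds that "Patients who exhibit objective disease progression prior to the end of cycle 1 will also be considered evaluable".

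Section 14.2 (sample size calculation) sets the analysis population: "All the patients enrolled in this phase will be included in the main analysis of response and PFS". For 6-month PFS it adds a rule for missing outcomes: "Patients who are lost to follow-up within 6 months are considered as failures for the PFS binary outcome". For response it says only that the rate will be calculated.

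The decision rules in Section 14.2 are numbers of patients. The trial continues after 28 patients if at least 3 respond or at least 5 are progression-free at 6 months. It is positive if at least 7 of 59 respond or at least 13 of 59 are progression-free at 6 months. Section 4.3 defines response as the best RECIST 1.1 response reached on study treatment, and says of stage I: "A total of 28 patients (including the first 15) will be enrolled during the first stage". Neither section provides for replacing patients.

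**The concern.** Read side by side, Sections 12.2 and 14.2 allow a patient to be in the response analysis without a response category. Such patients are foreseeable. The note to the best-response table in Section 12.43 describes patients with "global deterioration of health status requiring discontinuation of treatment without objective evidence of disease progression at that time". Others may stop for toxicity or withdraw before the first scheduled on-treatment scan at 8 weeks. Because the plan gives a failure rule for PFS and none for response, a reader may wonder whether the omission was meant, and whether the evaluable set is the intended denominator.

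The response proportion is half of the primary endpoint. A patient who is never re-imaged cannot be a responder, so dropping such patients can only raise the rate. Section 3.5 also says "we will consider this treatment worthy of further study if there is an observed response rate of 12.5"%, and at the minimum number of responders for a positive trial a few exclusions would move the observed rate across that figure.

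**Working it through.** **1. The plan's own figures.** Inputs from Section 14.2: response 5% under the null and 20% under the target, 6-month PFS 15% and 30%, stage I n = 28, bars 3 or 5, then 7 or 13. With R and S the numbers of responders and of patients progression-free at 6 months,

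P(positive) = 1 − P(R₁ < 3 and S₁ < 5) − P(continue, and at the end R < 7 and S < 13),

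summed exactly over the bivariate distribution. The joint probability is the product of the two rates (independent) or 0.90 × the smaller rate (correlated).

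| Null case | Plan | 28 + 30 = 58 | 28 + 31 = 59 |
|---|---|---|---|
| Type I error, independent | 0.10 | 0.0992 | 0.1086 |
| Type I error, correlated | 0.09 | 0.0904 | 0.0988 |
| Stop after stage I, independent | 49% | 0.4915 | 0.4915 |
| Stop after stage I, correlated | 55% | 0.5481 | 0.5481 |

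The plan's figures are reproduced with 58 patients. Sections 4.3 and 14.2 differ on whether the total is 58 or 59. That is a separate matter, so both totals are used below.

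**2. What an unassessed patient does to the decision.** The rules compare R with 3 and with 7. A patient with no re-evaluation adds 0 to R whether kept or dropped. R is unchanged, so the decision and the figures in step 1 are unchanged.

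**3. What exclusion would do to the reported rate.** With R responders, n enrolled and u unassessed, the rate moves from R/n to R/(n − u). The documents do not give u; the values here are assumptions. At R = 7:

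| Dropped | n = 58 | n = 59 |
|---|---|---|
| 0 | 7/58 = 12.1% | 7/59 = 11.9% |
| 2 | 7/56 = 12.5% | 7/57 = 12.3% |
| 3 | 7/55 = 12.7% | 7/56 = 12.5% |
| 6 | 7/52 = 13.5% | 7/53 = 13.2% |

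For 3 to 6 patients dropped, the shift is about 0.6 to 1.4 percentage points.

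**4. The 12.5% figure.** With nobody dropped, 7 responders already fall short of it (12.1% or 11.9%), although Section 14.2 calls that result positive. The mismatch is therefore between Sections 3.5 and 14.2 and does not come from unassessed patients. With 8 responders the figure is passed on all enrolled (8/58 = 13.8%, 8/59 = 13.6%). With 6 it would take 10 of 58 dropped (6/48 = 12.5%). Also, 12.5% is the midpoint of the null and target rates, (5 + 20)/2, just as Section 3.5's 22.5% for PFS is (15 + 30)/2. This suggests, though the text does not say so, a rounded description and not a second decision rule.

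**5. When type I error would move.** It would move if unassessed patients were replaced until the target number were evaluable. The null response rate among evaluable patients would then be 0.05/(1 − f), with f the assumed unassessed share: 5.3% at f = 5% and 5.6% at f = 10%. With 58 evaluable patients, type I error would go from 0.099 to 0.105 and 0.112 (independent), or from 0.090 to 0.094 and 0.099 (correlated). It would also move if the final bar were read as the proportion 7/59: 6 responders would then pass once 9 of 59 were dropped (6/50 = 12.0%), and a bar of 6 of 59 gives 0.140 or 0.123. The plan provides for neither; its bars are counts of patients enrolled.

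**The case for a change.** The best case for a change is that being included in an analysis is not the same as having a defined outcome in it. The authors wrote a failure rule for PFS and none for response. Section 12.2 is worded restrictively, and Section 14.2 describes stage I in terms of eligible patients who are evaluated, which could be taken as support for an evaluable-only denominator. One sentence would remove the doubt.

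The factual part stands: no sentence says that an unclassified patient is a non-responder. The inference does not. Section 12.2 says who receives a RECIST category and never makes that set the denominator of the primary rate, whereas Section 14.2 names response when it includes everyone enrolled. An evaluable-only primary rate would contradict that sentence.

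The two endpoints also differ in what they need. A patient lost before 6 months could be treated as censored or as progression-free, so PFS requires a rule. Response must be achieved to be counted, so a patient with no complete or partial response is already outside the numerator.

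The group at risk is also limited. Early objective progressors are evaluable, Section 9.1 calls for imaging at the end of study, Section 13.1 continues RECIST follow-up of patients without progression, and Section 12.43 gives symptomatic deterioration its own reporting label, which is not a response.

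A rewrite could also do harm. Limiting the primary set to eligible patients who start treatment would be narrower than the all-enrolled population now stated, and could raise the rate.

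**Conclusion.** The concern does not call for a change. Followed as written, the plan gives a response rate over all enrolled patients, with unassessed patients as non-responders, and that rate is not inflated. The stage I and final decisions, and the type I error of about 0.10 (independent) or 0.09 (correlated), do not depend on how these patients are labelled. A rise of roughly 0.6 to 1.4 percentage points at 7 responders would require an analyst to set aside the all-enrolled sentence and 3 to 6 patients to be unassessed; that number is assumed, not taken from the documents. What remains is a detail left unwritten that analysts would fill sensibly. The conclusion assumes that unassessed patients are not replaced, consistent with Sections 4.3 and 14.2, and that the bars are applied as counts.
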